### **8.6. Data Analysis**

All covariates will be summarized to get information about frequency distribution and mean, median or standard deviation. Numbers and percentages will be provided for categorical variables when performing descriptive analysis. Means, medians, standard deviations, or interquartile range as appropriate will be provided for continuous variables when performing descriptive analysis of continuous data.

Patients will be divided according to the mean of disease duration groups (below and above mean) and unadjusted comparisons between groups of the covariates and they will be evaluated using appropriate tests: chi-squared test will be used for categorical variables, t-test will be used for continuous variables, and the Kruskal-Wallis test for non-parametric variables; p-values will be generated.

We will determine the effect of early referral on the biologic treatment response patients with AS a multivariate analysis by using a stepwise linear regression model. The response variable is defined as BASFI and BASDAI at last visit. The baseline variables are considered demographic data, disease duration (years), methotrexate (yes/no), Current steroid therapy (yes/no), baseline BASFI, BASDAI, HLA-B27 positive (yes/no), anti-CCP (yes/no), present smoking (yes/no).

We will determine the effect of early response by using the difference in change between the baseline of BASDAI and BASFI and last follow-up. P-value <0.05 will be considered statistically significant.

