## 6. RATIONALE AND BACKGROUND

In the past 1–2 decades, treatment paradigms in Ankylosing Spondylitis (AS) have shifted dramatically from initial treatment with nonsteroidal anti-inflammatory drugs (NSAIDs), followed by the cautiously progressive addition of disease-modifying antirheumatic drugs (DMARDs), to the current treatment approach of the aggressive initiation of DMARD therapy soon after the diagnosis of AS has been made. This change in AS management results from increasing data supporting improved prognosis and outcomes with the initiation of DMARD therapy early in the course of symptomatic disease. Since the goals in AS management include not only disease remission but also improved functional status, which is strongly associated with radiographic joint damage, an understanding of the impact that the initiation of appropriate treatment during early AS has on these outcomes is essential.

Accurate diagnosis of early AS begins with clear definitions of AS, as there is considerable variability in the literature regarding the time frame defining early AS. Previous intervention studies in early AS have included early AS as disease duration from 3 months to 3 years; however, with the knowledge of improved outcomes with earlier treatment in AS, it becomes clear that a shorter time interval for classification of early rheumatoid arthritis (RA) is clinically significant. Due to the wide range of definitions of early AS presented in the literature, it is difficult to characterize the specific time frame that defines early AS.

Multiple studies have evaluated the benefits of early treatment of AS, including several that have evaluated the impact of early DMARD treatment on successful response to therapy. In particular, a meta-analysis of ~1,400 AS patients from 14 randomized controlled trials identified that one of the strongest predictors of response to therapy was a shorter disease duration at the time of treatment initiation.

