## 7. RESEARCH QUESTION AND OBJECTIVES

The objective of this study is to evaluate the impact of early initiation of etanercept on patient response compared to delayed introduction of biological treatment.

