#### 8.2.1. Inclusion Criteria

Patients must meet each of the following inclusion criteria to be eligible for inclusion in the study:

1. Diagnosed AS patients.
2.  $\geq 18$  years old.
3. Did not receive previous biological treatment for any reason.

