### **8.3. Data Sources**

Patients will be identified from the rheumatology patient registry with rheumatoid arthritis and will obtain information on patient demographics (age, gender), education level (years), present smoking status, disease duration (years), current steroid therapy (yes/no), baseline bath ankylosing spondylitis disease activity index (BASDAI), Bath Ankylosing spondylitis functional index (BASFI), human leukocyte antigen B27 (HLA-B27), anticitrullinated protein antibody (anti-CCP) status.

Primary Outcomes: Disease activity Index BASFI and BASDAI from the last follow-up visit.

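### Section 8.6 forms its only early and delayed groups at the sample's own mean disease duration, a cut not tied to the early-AS range cited in Section 6

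*Combined protocol and SAP*

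**What the plan says.** Section 7 gives the aim as to "evaluate the impact of early initiation of etanercept on patient response compared to delayed introduction of biological treatment". Section 8.1 words its primary objective as early against delayed management.

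Section 6 discusses what early means. It reports that "Previous intervention studies in early AS have included early AS as disease duration from 3 months to 3 years". It then says that "it becomes clear that a shorter time interval for classification of early rheumatoid arthritis (RA) is clinically significant" (the sentence names RA, although the topic is AS), and concludes that "it is difficult to characterize the specific time frame that defines early AS". It adopts no threshold.

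Section 8.6 contains the only rule that forms groups: "Patients will be divided according to the mean of disease duration groups (below and above mean". It attaches this rule to unadjusted comparisons of covariates. The effect of early referral is then assigned to a stepwise linear regression of BASFI and BASDAI at the last visit, with these candidates: "The baseline variables are considered demographic data, disease duration (years), methotrexate (yes/no", and others. A closing sentence adds an analysis of change from baseline to last follow-up but does not say which groups are compared.

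Eligibility sets no limit on disease duration. The first inclusion criterion in Section 8.2.1 is simply "Diagnosed AS patients". Section 8.3 lists the variable among the data to be obtained ("disease duration (years), current steroid therapy (yes/no") without saying at what date it is measured. Section 8.4 sets no study size.

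**The concern.** An early-versus-delayed question needs a definition of early that does not depend on who happens to be in the dataset. A split at the sample mean does not supply one. The cut is unknown until the data are assembled and moves as patients are added or removed. Disease duration is usually right-skewed, so a few very long durations raise the mean and widen the early group. At a sample mean of 8 years, a patient treated after 7 years of disease would count as early.

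This affects how either result can be read. A null contrast could mean that early initiation does not help, or that few patients in the early group were early in the sense Section 6 discusses. A positive contrast would support only a statement about patients below X years, where X belongs to this sample. Section 8.8 names missing data as the only limitation, so a reader of the results would not be warned.

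**Working it through.** **No figure to reproduce.** The documents state no mean, SD or distribution of disease duration, and no sample size or power. The question is what the rule in Section 8.6 can produce over a plausible range.

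**Inputs**
- Cut: the sample mean, m (Section 8.6).
- Reference point: 3 years, the upper end of the range cited in Section 6.
- Assumed, not in the documents: lognormal duration, m from 3 to 10 years, CV c = 0.7, 0.9 and 1.1.

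**Formulas.** σ² = ln(1 + c²) and μ = ln(m) − σ²/2.
- Share of all patients labelled early: F(m) = Φ(σ/2).
- Share of the early group beyond 3 years: 1 − F(3)/F(m) for m > 3, and 0 for m ≤ 3.
- Share of all patients who would be early under a fixed 3-year cut: F(3).

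**Worked case, m = 8, c = 0.9.** σ² = ln(1.81) = 0.593, σ = 0.770, μ = 2.079 − 0.297 = 1.783. F(8) = Φ(0.385) = 0.650. F(3) = Φ((1.099 − 1.783)/0.770) = Φ(−0.888) = 0.187. The share beyond 3 years is 1 − 0.187/0.650 = 0.71.

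**Results over CV 0.7 to 1.1**

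| Sample mean (years) | Early group beyond 3 years |
|---|---|
| 3 or less | 0% |
| 4 | 18-29% |
| 5 | 33-50% |
| 6 | 45-65% |
| 8 | 62-83% |
| 10 | 73-91% |

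F(m) does not depend on m, so the mean split labels 62-67% of patients early throughout.

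**Sensitivity to shape.** With gamma as well as lognormal durations and CV 0.5 to 1.0, the ranges widen to 17-40% at a mean of 4, 29-66% at 5, 38-82% at 6, 51-94% at 8 and 59-98% at 10. More than half of the early group is beyond 3 years once the mean passes about 4.3-4.5 years (CV 0.5), 5.2-5.8 (CV 0.75) or 6.1-7.9 (CV 1.0).

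**Cost of a fixed 3-year cut.** F(3) is 11-26% of patients at a mean of 8 years and 6-18% at a mean of 10 (lognormal, CV 0.7 to 1.1).

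**The regression.** Duration enters in years, so the mean does not matter there. Three gaps remain:
- Stepwise selection may drop the term.
- A linear term assumes the same change in outcome per year at every duration.
- Section 8.3 and Section 8.6 do not say whether duration is counted to the first etanercept dose, to referral or to data extraction. Unless it is counted to the first dose, it does not measure time to initiation.

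**The case against.** The strongest reply is that the mean split is mostly descriptive. Section 8.6 ties it to unadjusted covariate comparisons and gives the effect of early referral to the regression, where duration has no cut. If benefit declines gradually with duration, a continuous term does address earlier against later initiation. This largely stands. A reader might infer that the whole plan fails to test early initiation, and the documents do not support that. What remains is that no other early and delayed groups exist for the objective or for the change-from-baseline analysis, which names no groups and may use this split.

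A reader might also infer that the protocol breaches its own 3-year limit. It has none. Section 6 reports a range from other studies, argues for something shorter, and says the time frame is hard to define. Three years is a reference point only, and a 3-year cut might itself be too long.

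Nor do the documents show that the early group will consist mostly of long-duration patients. They give no durations, and at a mean of 3 years or less the problem disappears.

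Finally, one could argue that the contrast is diluted to a fraction of its true size. If all benefit stopped abruptly at 3 years, a 1.0-point BASDAI benefit would appear as 1.0 × (1 − 0.71) = 0.29 at a mean of 8 years and CV 0.9. At a mean of 4 years, the same arithmetic keeps 0.71-0.82 points. Nothing in the documents supports such a step. Section 6 cites shorter duration as a predictor of response, which fits a gradient equally well.

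**Conclusion.** The concern holds for the mean-split contrast. Its cut is set by the sample, is not tied to the range in Section 6, and may separate shorter from longer disease rather than early from delayed initiation. How far it does so depends on a mean that the documents do not give: under the lognormal assumption, from none of the early group beyond 3 years (mean of 3 years or less) to 73-91% (mean of 10 years). The structural point needs no assumption, since no fixed definition of early appears anywhere in the plan.

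The regression partly avoids the problem, but it does not guarantee that duration is kept, that its effect is modelled flexibly, or that it is measured at treatment start. The plan should be changed. The size of any resulting bias in the treatment comparison cannot be stated from the documents.

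**What to change.** In Section 8.6:

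1. Define disease duration at the first etanercept dose, and state its starting point (symptom onset or diagnosis).
2. Force it into the BASDAI and BASFI regressions as a continuous term that allows curvature (for example a quadratic or spline term), exempt from stepwise selection. Make this the main exposure analysis.
3. Report alongside it an early/delayed contrast at a fixed cut justified from Section 6, for example 3 years or less, the upper end of the cited range.
4. Keep the mean split as a descriptive table only, and say which grouping the change-from-baseline analysis uses.

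Section 5 planned the end of data collection for 01 October 2020, and this version is dated 29 July 2021, so the data may already have been seen. If so, the fixed cut should be labelled post hoc.

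Cost: a wording change and modest recoding, because disease duration is already among the variables to be obtained. Duration at first dose may have to be derived from dates. The fixed-cut early group could be small (about 11-26% of patients at a mean of 8 years under the same assumptions), so its interval would be wide. That is why the continuous analysis should lead.

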## 8. RESEARCH METHODS

### 8.1. Study Design

- **Retrospective analysis** of patients with AS that received etanercept from Baghdad teaching hospital (Rheumatology center) from August 2012 until March 2020 (inclusion and exclusion criteria will apply for selecting patients).
- **Primary objective:** determine the clinical impact of early referral for management in patients with AS compared to delayed management.
- **Secondary objective:** determine the influence of early referral on the response to biological treatment.

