#### Hypothesis

There is no difference in response between early and delayed referral to biological treatment.

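### The only adjusted analysis of early versus delayed referral is a stepwise regression that can drop disease duration itself, or a confounder such as age

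*Combined protocol and SAP*

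**What the plan says.** Section 8.6 contains three comparative analyses.

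1. Patients are split at the mean disease duration, and the two groups are compared by "unadjusted comparisons between groups of the covariates", using chi-squared, t or Kruskal-Wallis tests.
2. The effect of early referral on response is to come from "a multivariate analysis by using a stepwise linear regression model". The responses are BASFI and BASDAI at the last visit. The candidate list reads "The baseline variables are considered demographic data, disease duration (years), methotrexate (yes/no), Current steroid therapy (yes/no), baseline BASFI, BASDAI", followed by HLA-B27, anti-CCP and smoking.
3. Change from baseline to last follow-up is compared, with no model or covariates stated.

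The section closes with "P-value <0.05 will be considered statistically significant", which is not tied to entry into or removal from the model. The hypothesis in Section 8.2 is "There is no difference in response between early and delayed referral to biological treatment". The stepwise analysis closely matches the secondary objective in Section 8.1, to "determine the influence of early referral on the response to biological treatment". Section 8.3, however, names as primary outcomes "Disease activity Index BASFI and BASDAI from the last follow-up visit", which are the same responses. Section 8.4 sets no sample size, Section 8.8 lists only missing data as a limitation, and Annex 1 lists no stand-alone document that could hold further model rules.

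**The concern.** Exposure is not randomised, so an adjusted model is the only place where early and delayed patients can be compared on like terms. Stepwise selection treats the exposure as one more predictor. Four things can follow from the text as it stands:

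- Duration is dropped, and there is no adjusted estimate or interval for the study's hypothesis.
- A confounder related to duration, such as age, is dropped. The duration coefficient then absorbs part of that confounder's effect, and its 5% test no longer holds its level.
- The BASFI and BASDAI models end with different covariates, so the two results are adjusted for different things.
- The baseline score is kept in one model and dropped in another. Duration accrues before the baseline score, so this need not bring back confounding. It does change the question, from duration given the baseline score to duration overall, and the plan would not say which was answered.

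The first consequence needs no simulation: it follows from where duration sits in the candidate list.

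**Working it through.** **No figure to reproduce.** The plan gives no sample size, SD, effect size or selection threshold. Every numerical input below is an assumption, and the results show what can happen, not what did happen in this study.

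**Assumed inputs.** Duration SD 6 years; age SD 10 years; duration-age correlation 0.5; baseline BASFI and BASDAI SD 1.8, correlated 0.6 with each other and 0.3 with duration; own-baseline coefficient 0.4; residual SD 1.8; error correlation between the two scores 0.6. Education (SD 4 years) and six independent binary covariates have no effect. Stepwise is bidirectional, entry p<0.05 and removal p>0.10. The fixed model has 11 terms. Runs per cell: 10,000 with no duration effect, 5,000 with one.

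**Closed-form checks.** These also take an age-baseline correlation of 0.15.

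- *Omitting age.* Bias in the duration slope = age effect × slope of age on duration = 0.025 × (0.5 × 10/6) = 0.025 × 0.833 = 0.021 points per year, about half of a true slope of 0.04. Its sign is that of the age effect times that of the age-duration association.
- *Omitting the baseline scores.* Shift = 0.4 × (0.3 × 1.8/6) = 0.4 × 0.09 = 0.036, so a slope of 0.040 becomes 0.076. The simulation gave 0.040 and 0.076.
- *Precision of the fixed model.* The R² of duration on age and the two baseline scores is 0.315. SE = 1.8 / (6 × √(df × 0.685)) with df = n − 12, which gives 0.0386/0.0264/0.0184. The 95% CI half-widths are 0.077/0.052/0.036, as simulated.

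**Simulated results**

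| | n=100 | n=200 | n=400 |
|---|---|---|---|
| *No duration effect: duration called significant* | | | |
| No age effect: stepwise | 5.0% | 4.8% | 4.6% |
| No age effect: fixed | 4.7% | 5.4% | 5.0% |
| Age +0.025/year: stepwise | 7.1% | 7.7% | 7.7% |
| Age +0.025/year: stepwise, only duration forced in | 10.8% | 11.9% | 11.9% |
| Age +0.025/year: fixed | 4.9% | 4.9% | 4.8% |
| Age −0.025/year: stepwise | 7.0% | 7.7% | 7.4% |
| Age −0.025/year: fixed | 5.5% | 4.7% | 4.9% |
| *Duration slope 0.04, age +0.025* | | | |
| Duration dropped from BASFI model | 68% | 54% | 37% |
| Duration dropped from both models | 54% | 38% | 23% |
| Fixed model significant | 18% | 32% | 59% |
| BASFI and BASDAI models differ in terms other than baseline scores | 67% | 67% | 68% |
| *Duration slope 0.08, age +0.025* | | | |
| Duration dropped from BASFI model | 29% | 11% | 1% |

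In 90/82/68% of the stepwise false positives at age +0.025, age had been dropped, which identifies the mechanism.

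**Sensitivity, no duration effect, n = 100 and 200.** The grid varied the age effect (0, ±0.025, +0.04), the duration-age correlation (0.3 to 0.7) and the thresholds (0.05/0.10 and 0.15/0.15). Over 36 settings with an age effect, stepwise false positives were 5.2–14.6% and fixed 4.5–5.7%. Over 12 settings without one, stepwise gave 4.2–6.9% and fixed 4.5–5.4%.

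**A different algorithm.** Backward elimination at p<0.05, with standardised effects of 0.15 for both duration and age, dropped duration in 59/46/27% of runs. With no duration effect it called duration significant in 9.4/9.2/6.8%, against 5.4/4.8/4.9% for the full model.

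**Baseline score.** Stepwise dropped the score's own baseline in 52/27/7% of runs when its coefficient was 0.2, in 7/0.4/0% at 0.4, and in under 1% at 0.6.

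**Not claimed.** Stepwise did not consistently exaggerate significant estimates more than the fixed model. Given p<0.05 at slope 0.04, the means were 0.090 against 0.093, 0.071 against 0.069, and 0.056 against 0.052 (stepwise against fixed).

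**The case against.** The best counter-argument is that the drop rates mostly measure low power. At slope 0.04 the fixed model is itself non-significant in 82/68/41% of runs, and in a re-run duration was dropped while the fixed model was significant in only about 0.8% of runs at n = 100 and 200. A drop therefore rarely hides a detectable effect. This stands, and the drop rates should be read with it in mind. What is lost is the estimate and its interval, which a study with this single question cannot do without; the fixed model always reports them.

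Second, the inflation depends on an assumed age effect, and without one it disappears. Also true. The severity rests on the exposure being droppable, not on the size of the inflation.

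Third, the plan names no selection criterion, so it need not be a p-value. P-value selection is the usual meaning of stepwise, but an information criterion could drop the same terms, and the silence is part of the problem.

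Fourth, keeping the whole covariate list is heavy with no sample size set, and steroid and methotrexate use may, like the baseline scores, partly follow from longer disease. The caveat on those two is fair and is carried into the fix. The cost in precision is small: adding education moved the half-width at n = 100 from 0.076 to 0.077.

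Finally, the data were probably already collected, so any new model is post hoc. That calls for disclosure; it does not make the stepwise result a sound main analysis.

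**Conclusion.** The concern holds and must be fixed. As written, the plan's only adjusted analysis can omit the study's only exposure or a genuine confounder, and neither of the other two comparisons in Section 8.6 is described as adjusted. That conclusion rests on the text alone.

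The size is illustrative. Under the assumed inputs, duration is absent from the BASFI model in roughly one third to two thirds of runs at a slope of 0.04. The false-positive rate is about 7–8% where age has a modest effect, and is not inflated where it has none. Forcing in duration alone is not enough: with the other terms still selected, the rate rose to 10.8–11.9%.

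**What to change.** In Section 8.6, make the main adjusted analysis one fixed linear model for each last-visit score. Include disease duration in years, baseline BASFI, baseline BASDAI, age, gender, present smoking, current steroid therapy, methotrexate, HLA-B27 and anti-CCP, all kept whatever their p-values. Report the duration coefficient with its 95% CI regardless of significance. In addition:

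- Settle two items in the variable lists. Section 8.3 gives "patient demographics (age, gender), education level (years), present smoking status, disease duration (years), current steroid therapy (yes/no", so education stands apart from age and gender, and Section 8.6 does not name it; say whether it counts as demographic data. Methotrexate is in Section 8.6 but not in Section 8.3; add it there, or remove it from both models if the registry does not hold it.
- Fit the same model with the below/above-mean group in place of years, as a second presentation.
- State that the estimate is conditional on the baseline scores, which may partly reflect the delay, and show the model without them as a sensitivity analysis. Note the same caveat for steroid and methotrexate use.
- Show the stepwise result alongside, labelled exploratory.
- State that the change followed data collection, and whether results had been seen. Collection was planned to end on 01 October 2020, this version is dated 29 July 2021, and Section 4 records milestones being aligned with the study report.

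The cost is a rewritten model paragraph and one line in Section 8.3. The model uses 10 degrees of freedom, or 11 with education. No new data are needed beyond confirming methotrexate.

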**PFIZER CONFIDENTIAL**

## 5. MILESTONES

Milestone	Planned date
Start of data collection	01 August 2020
End of data collection	01 October 2020
Final study report	01 September 2021

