### 8.2. Setting

#### Patients and Methods

Data will be collected from the Baghdad Teaching Hospital registry. The rheumatology patient registry is a prospective longitudinal multicenter cohort initiated in 2012. It captures all patients treated with biologic therapies managed in the rheumatology department. The decision to initiate and maintain the treatment is guided by the American College of Rheumatology (ACR) recommendations.

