#### Study population

Patients will be included in the study if they met the American College of Rheumatology/The European League Against Rheumatism (EULAR) 2019 criteria for AS, with at least 1 year of follow up after starting their first biologic therapy.

Exclusion criteria: patients previously or currently treated with other biological therapies.

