### **8.2.2. Exclusion Criteria**

Patients meeting any of the following criteria will not be included in the study:

1. Patients previously or currently treated with other biological therapies.
2. Use of etanercept for less than 1-year duration.

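### Etanercept starts span roughly 6.7 years, but no start date is extracted and no outcome model includes calendar year of start, so the early-versus-delayed contrast is unadjusted for era of care

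*Combined protocol and SAP*

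**What the plan says.** - **Window.** Section 8.1 takes patients treated at the centre "from Baghdad teaching hospital (Rheumatology center) from August 2012 until March 2020". Section 8.2 describes the source: "The rheumatology patient registry is a prospective longitudinal multicenter cohort initiated in 2012".
- **Minimum follow-up and exposure.** The study population paragraph requires patients "with at least 1 year of follow up after starting their first biologic therapy". Section 8.2.2 excludes "Use of etanercept for less than 1-year duration". Section 5 gives "End of data collection 01 October 2020".
- **Exposure.** Section 8.6 splits patients at the mean disease duration and also enters disease duration in a stepwise linear regression.
- **Outcome.** BASDAI and BASFI at the last follow-up visit, and their change from baseline.
- **Covariates.** Demographics (age and gender in Section 8.3), then "disease duration (years), methotrexate (yes/no), Current steroid therapy (yes/no), baseline BASFI, BASDAI, HLA-B27 positive (yes/no"), anti-CCP and present smoking. The change-from-baseline comparison names no covariates.
- **Calendar time.** It appears in no data item in Section 8.3 and no analysis in Section 8.6. Section 8.8 names only missing data as a limitation.
- **Background.** Section 6 says that AS management has moved over one to two decades "to the current treatment approach of the aggressive initiation of DMARD therapy soon after the diagnosis of AS has been made".

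**The concern.** The comparison groups are formed by disease duration, and patients start etanercept at different times over a period of more than six years. Calendar year of start confounds the comparison if two things hold together:

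- disease duration at start drifts over the window, so that the early and delayed groups differ in mean start year;
- outcome drifts with calendar time for reasons other than how early treatment was begun, such as better background care.

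Part of the group difference would then be an era effect reported as an effect of early initiation. Section 6 makes it reasonable to ask whether practice was changing. The listed covariates describe the patient at baseline and do not represent the care given afterwards. Because selection is stepwise, even listed variables may drop out. As planned, the analysis gives a reader no means of telling whether era matters.

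**Working it through.** The plan states no sample size, SD, effect size or power, so there is no figure of its own to reproduce.

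**1. Span of starts (from the documents).** Read the Section 8.1 window as bounding both first start and last follow-up.
- Latest start: March 2020 − 1 year = March 2019. From August 2012 that is about 6.7 years, with possible follow-up from 1 to about 7.7 years.
- If follow-up counts to the end of data collection: 1 October 2020 − 1 year = October 2019, a span of about 7.2 years.

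The point is the same under either reading.

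**2. Bias formula.** Spurious difference = (secular change in outcome per calendar year) × (difference between groups in mean start year). If either factor is zero, the bias is zero.

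**3. Illustrative inputs (all assumed, none from the documents).** Starts uniform over the window; log-normal disease duration with coefficient of variation 0.9; outcome SD 2.0 points; split at the sample mean; no true effect of duration; two-sided alpha 0.05. The secular change is taken as an improvement.

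| Mean duration at start, first to last | Early group starts later by | Bias at 0.1 points/year | Bias at 0.3 points/year |
|---|---|---|---|
| 10 → 6 years | 0.6 years | 0.1 × 0.6 = 0.06 | 0.3 × 0.6 = 0.18 |
| 12 → 5 years | 0.95 years | 0.1 × 0.95 ≈ 0.10 | 0.3 × 0.95 ≈ 0.29 |
| No trend | 0 | 0 | 0 |

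**4. Simulated type I error on those inputs.**
- At 0.1 points per year: about 4–7% for n = 200 to 400, with about 8% in the steepest-drift case at n = 400.
- At 0.3 points per year: about 9% (n = 200) and 13% (n = 400) for 10 → 6 years; about 14% and 26% for 12 → 5 years. Independent runs differ by a point or two, so 9–25% is a fair summary.
- With disease duration entered as a continuous variable, as in the regression: 9–28% at 0.3 points per year. Dropping the mean split does not remove the problem.
- With start year in the model: about 5% (4–6%) in every setting.
- With no duration trend: nominal with or without start year.

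**5. How strong the 0.3 assumption is.** 0.3 × 6.66 years = 2.0 points over the window, a full assumed SD on the same drug. That is the upper end of the illustration, not an expected value.

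**The case against.** The strongest reply is that nothing in the documents shows a trend at this centre, and that several stronger readings do not hold.

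- **Section 6 might be read as documenting the confounding.** It does not. Its link to better outcomes runs through early treatment, which is the exposure under study. It describes DMARD therapy in general over one to two decades, and it gives no size and no data for this centre. A confounder needs another route to the outcome, and Section 6 states none.
- **A reader might infer that the bias must favour early initiation.** The direction is not established. For instance, if response grows with time on drug, later starters would look worse at their last visit.
- **A reader might think that a limited start window ties delay to era automatically.** A limited window ties onset date to delay. It does not correlate start year with delay; that needs an actual trend in duration.
- **Restricting by onset date might look like a remedy.** It does not suit a split at the mean. In the illustrations the mean is about (10 + 6)/2 = 8 or (12 + 5)/2 = 8.5 years. With starts ending in March 2019, onset after about March 2011 cannot give a duration above 8 years. An onset window chosen around a 3-year delay (August 2009 to March 2016) would leave only about 1–2% of its patients in the delayed group.
- **Outcome timing weakens the concern.** Patients still followed have last visits near a common data cut, so care at assessment is largely shared. Start year then stands partly for follow-up length. Baseline BASDAI, BASFI, methotrexate and steroid use capture some of the care before the start.

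All of this stands as a limit on size and certainty. It does not alter the fact that start year is neither extracted nor modelled, or that modelling it restores the nominal error rate wherever a trend exists.

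**Conclusion.** The gap is real: starts span about 6.7 years (about 7.2 on the later cut), and no planned analysis can separate early initiation from era of care. Whether bias results depends on two trends about which the documents are silent, so neither its size nor its direction can be set from them. On the assumed inputs the spurious difference is 0 to about 0.3 points. The error rate is near nominal for a slow secular change and clearly inflated only for a fast one combined with falling disease duration. This is a cheap improvement that makes the main comparison easier to defend. It is not evidence that the comparison is biased.

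**What to change.** 1. Add the etanercept start date to the Section 8.3 data items. The 1-year rule already needs it or an equivalent. State also that disease duration is measured at that date, which the plan leaves open.
2. In Section 8.6, force calendar year of start into each outcome model for BASDAI and BASFI, including the change-from-baseline comparison. Do not leave it to stepwise selection.
3. Model follow-up time as well, because with a last-visit outcome it is correlated with start year. If most last visits fall near the data cut, the two may be hard to separate; an outcome at a fixed time after start would then be the clearer choice.
4. Tabulate disease duration by start year, and report the early-versus-delayed estimate with and without start year.

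**Cost.** One degree of freedom for start year, a further term for follow-up time, and some collinearity between them that may widen the intervals. If there is no trend, the two estimates will be close, and the report can say that start year does not explain the result.
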